6.2.1. Permitted Medications

- Medications not specifically excluded in [Section 6.2.2](#) may be taken as necessary.
- Concomitant treatment with antibiotics at the discretion of the Investigator is allowed.
- Medications routinely administered and not explicitly prohibited in this protocol used prior to and following uncomplicated cataract surgery are allowed. These medications will be collected in the source and eCRF as indicated for routine cataract surgery and are not expected to be associated with treatment for AEs unless otherwise indicated.

6.2.2. Medications Not Permitted

Use of the following medications is not allowed during the study and for the timeframes specified:

Within 2 days prior to surgery (Visit 2) and for the duration of the study:

- Ocular NSAIDs
- Systemic NSAIDs with the exception of ≤ 81 mg/day of acetylsalicylic acid (ASA or aspirin)
- Mast cell stabilizers
- Antihistamines
- Decongestants

- All eye drops (except antibiotic eye drops considered to be included in post cataract surgery standard of care treatment)
- Glaucoma medications
- All topical ophthalmic gels or artificial tears
- TNF-blocking agents (e.g., etanercept, adalimumab, infliximab)

Within 7 days prior to surgery (Visit 2) and for the duration of the study:

- Topical eyelash growth medications

Within 14 days prior to surgery (Visit 2) and for the duration of the study:

- Systemic or ocular corticosteroids other than study product (except stable maintenance dose of inhaled or intranasal corticosteroids)

Within 30 days prior to surgery (Visit 2) and for the duration of the study:

- Ocular immunosuppressant (e.g., Restasis[®])
- Other investigational products

Within 6 months prior to the screening visit (Visit 1) alterations to the dose of the following are disallowed:

- Anticholinergics
- Antidepressants (stable dose of PRN treatment acceptable)
- Systemic immunosuppressive agents
- Oral steroids (dose must be less than 11 mg/day)

NOTE: Dose must remain stable throughout the course of the study

If using nutraceuticals or multivitamins, subjects may not alter their stable dose throughout the study.

6.3. STUDY PRODUCT USE COMPLIANCE

Compliance will be assessed by comparing study product accountability records with the dosing information recorded daily by the subject. The site will document this comparison along with verification of the numbers of used and unused study product bottles. The numbers of missed doses as assessed at each clinic visit should be documented in the eCRF.

6.4. DRUG ACCOUNTABILITY

Sponsor study monitors or designees will conduct accountability of study product (KPI-121 or placebo). Accountability will be ascertained by performing reconciliation between the amount of drug sent to the site and the amount unused at the time of reconciliation.

Clinical trial materials will be shipped to the investigational sites under sealed conditions. Study product shipment records will be verified by comparing the shipment inventory sheet to the actual quantity of drug received at the site. Accurate records of receipt and disposition of

the study product (e.g., dates, quantity, subject number, dose dispensed, returned) must be maintained by the Investigator or his/her designee. Study product will be stored at controlled room temperature (15-25°C/59-77°F) in an area limited with controlled access.

At the end of the study, all study materials, including any unused study product (KPI-121 drug product or placebo), as well as original containers (even if empty), will be returned to the drug packaging vendor in accordance with sponsor or designee's standard operations procedures (SOPs), following approval by the Sponsor. All returns of study product will be documented. The study monitor or designee will verify drug accountability. All drug accounting procedures must be completed before the study is considered complete.

6.5. MAINTENANCE OF RANDOMIZATION AND PROCEDURE FOR BREAKING THE CODE

The sponsor, the project teams at the designated Contract Research Organizations (CROs), and investigative staff responsible for assessments of study endpoints will be masked to study product assignments. In case of medical emergency, or occurrence of an SAE, the randomization code may be unmasked and made available to the Investigator, sponsor, and/or other personnel involved in the monitoring or conduct of this study. In the absence of medical need, the randomization code will not be available to the above individuals until after the study is completed and the database is locked.

In the event of a medical need, the Investigator will treat each subject as needed. Since there is no specific antidote to KPI-121, immediate emergency unmasking is not necessary. If the Investigator feels it is necessary to unmask a subject's assignment after an emergency situation, the Investigator may call the medical monitor and notify the sponsor. The study product assignment will be revealed on a subject-by-subject basis with the approval of the medical monitor and sponsor, thus leaving the masking of the remaining subjects intact.

A randomization code will be computer-generated by D.A.T.A., Inc. or designee. Randomization team members will work independently of other team members at the CRO. Study personnel, study subjects, the sponsor, and project teams at the CROs involved in the study will be masked to study product assignments.

7. ASSESSMENT OF EFFICACY

Efficacy Assessments include the following:

- Slit Lamp Biomicroscopy examination of the following ocular signs of inflammation:
 - Signs of anterior ocular inflammation (i.e., cells; 0-4 Scale)
- Subject-Rated Ocular Pain Assessment (0-5 Scale)
- Rescue therapy

8. ASSESSMENT OF SAFETY

8.1. SAFETY PARAMETERS

Safety parameters include:

- Assessments of AEs
- Snellen Distance VA by Pinhole Method
- Slit Lamp Biomicroscopy including assessment of the following signs of inflammation: Palpebral conjunctival erythema, corneal edema, hyphema, ciliary flush, bulbar conjunctival injection
- IOP Measurement
- Dilated Ophthalmoscopy

8.2. ADVERSE EVENT DEFINITIONS

Adverse Event (AE): Any untoward medical occurrence associated with the use of an investigational product in humans, whether or not considered drug related.

Adverse Reaction (AR): any AE caused by a drug. Adverse reactions are a subset of all suspected adverse reactions where there is reason to conclude that the drug caused the event.

Suspected Adverse Reaction (SAR):

Any AE for which there is a reasonable possibility that the drug caused the AE. For the purposes of IND safety reporting, “reasonable possibility” means there is evidence to suggest a causal relationship between the drug and the AE. A SAR implies a lesser degree of certainty about causality than adverse reaction, which means any AE caused by a drug.

Unexpected: An AE or SAR is considered "unexpected" if it is not listed in the Investigator’s Brochure or is not listed at the specificity or severity that has been observed; or, if an Investigator’s Brochure is not required or available, is not consistent with the risk information described in the general investigational plan or elsewhere in the current application.

Life-threatening: An AE or SAR is considered “life-threatening” if, in the view of either the Investigator or sponsor, its occurrence places the patient or subject at immediate risk of death. It does not include an AE or suspected adverse reaction that, had it occurred in a more severe form, might have caused death.

NOTE: Events that are related and expected due to uncomplicated cataract surgery should not be classified as an AE.

A **SERIOUS ADVERSE EVENT (SAE)** is any AE or suspected adverse reaction occurring at any dose that:

- Results in death.
- Is life-threatening.
- Results in a persistent or significant incapacity or substantial disruption of the ability to conduct normal life functions.
- Requires inpatient hospitalization.
- Prolongs inpatient hospitalization.
- Is a congenital anomaly/birth defect.
- Is a significant medical event (i.e., one that may jeopardize the subject or may require intervention to prevent one or more of the other outcomes listed above).

A **NON-SERIOUS ADVERSE EVENT** is any AE that does not meet the definitions for SAEs as described above.

Each AE will be classified as **SERIOUS or NON-SERIOUS** using the definitions provided above.

The **SEVERITY** of each AE will be classified as **MILD, MODERATE, or SEVERE**.

The Investigator will review each event and assess its **RELATIONSHIP** to use of study product (unrelated, unlikely, possibly, probably, definitely). The AE will be assessed using the following definitions:

Unrelated:

- Event occurring before dosing.
- Event or intercurrent illness due wholly to factors other than study product use.

Unlikely:

- Poor temporal relationship with study product use.
- Event easily explained by subject's clinical state or other factors.

Possible:

- Reasonable temporal relationship with study product use.
- Event could be explained by subject's clinical state or other factors.

Probable:

- Reasonable temporal relationship with study product use.
- Likely to be known reaction to agent or chemical group, or predicted by known pharmacology.
- Event cannot easily be explained by subject's clinical state or other factors.

Definite:

- Distinct temporal relationship with study product use.
- Known reaction to agent or chemical group, or predicted by known pharmacology.
- Event cannot be explained by subject's clinical state or other factors.

8.3. PROCEDURES FOR AE REPORTING BY THE INVESTIGATOR

Typically, the time that the informed consent is signed by the subject is designated as the start of safety data collection.

If a subject will not formally enter a trial until several days or longer after the informed consent is signed, the day of randomization to treatment may be a more appropriate time to begin collecting safety information. AEs occurring prior to randomization may be more appropriately considered medical history or pre-existing conditions.

AEs will be monitored throughout the study and will be recorded on the CRF with the date and time of onset, date and time of resolution, intensity, seriousness, causality (relationship to use of study product), treatment required, and the outcome.

To elicit AEs, simple questions with minimal suggestions or implications should be used as the initial questions at all evaluation points during the trial. For example:

- How have you felt since your last assessment?
- Have you had any health problems since your last assessment?

The severity of each AE should be categorized as mild, moderate, or severe.

The causality of use of study product in relation to the AE will be assessed by the Principal Investigator after careful medical consideration and categorized as unrelated, unlikely, possible, probable, or definite.

If an AE occurs, the Investigator will institute support and/or treat as deemed appropriate. If a non-SAE is unresolved at the time of the last day of the study, an effort will be made to follow up until the AE is resolved or stabilized, the subject is lost to follow-up, or there is some other resolution of the event. The Investigator should make every attempt to follow SAEs to resolution.

Expected changes resulting from routine uncomplicated cataract surgery will not be captured as AEs. Likewise, the presence of inflammation due to surgery is not an AE but rather the condition under investigation.

8.4. SERIOUS ADVERSE EVENT REPORTING BY THE INVESTIGATOR**Serious Adverse Event Reporting**

It is the responsibility of the Investigators or their designees to report any event of this nature to the sponsor or a designee within 24 hours of the event being brought to the Investigators' or their staffs' attention. It is also the responsibility of the Investigator to report all SAEs

reported at their site to their Institutional Review Board (IRB), as required. The Investigator should make every attempt to follow all SAEs to resolution.

The following information should be provided when an SAE is reported to the sponsor or designee:

1. Protocol Number
1. Site Number
2. Subject Number
3. Subject Demographic information, including:
 - Date of Birth
 - Sex
 - Race
4. Study product start date
5. Date of last dose of study product
6. Date study product reinitiated (if study product interrupted)
7. SAE information, including:
 - SAE term (diagnosis only; if known or serious signs/symptoms)
 - Description of SAE/narrative
 - Date/time of onset
 - Severity
 - Outcome
 - Date/time of resolution or death (if duration < 24 hours)
 - Relationship to study product
 - Action taken with study product
8. Criteria for classifying the event as serious, including whether the SAE:
 - Resulted in death.
 - Was life-threatening
 - Required inpatient hospitalization.
 - Prolonged inpatient hospitalization.
 - Resulted in a persistent or significant incapacity or substantial disruption of the ability to conduct normal life functions.
 - Was a congenital anomaly/birth defect

- Important medical events that may not result in death, were not life-threatening, or did not require hospitalization may be considered serious when, based upon appropriate medical judgment, they may jeopardize the patient or subject and may require medical or surgical intervention to prevent one of the outcomes listed in this definition. Examples of such medical events include allergic bronchospasm requiring intensive treatment in an emergency room or at home, blood dyscrasias or convulsions that do not result in inpatient hospitalization, or the development of drug dependency or drug abuse.

9. Concomitant medications
10. Relevant history
11. Possible causes of SAE other than study product
12. Copy of AE page from the CRF

NOTE: If an SAE occurs in any study involving KPI-121 that is unexpected and is determined to be related or possibly related to study product, all sites will be notified by the sponsor and each site should report it to their IRB.

8.5. RESCUE THERAPY

Any subjects not responding adequately to the study medication may be rescued and placed on alternate therapy at the Investigator's discretion at any time. The choice of rescue medication is at the Investigator's discretion. Any subject placed on rescue therapy will discontinue use of the study medication and continue study participation through Visit 7.

Rescued subjects will be considered treatment failures, but the need for rescue therapy will not be considered an AE. Rescued subjects experiencing an AE at the time of rescue will be followed through stabilization or resolution of the AE or the end of the study (whichever comes last).

9. STATISTICS

9.1. STATISTICAL METHODS

Continuous measures (e.g., age) will be summarized descriptively by the mean, standard deviation, median, minimum and maximum values. Categorical measures will be summarized by the number and percent of subjects.

If the two placebo groups demonstrate no statistically significant difference, they will be pooled for analysis.

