1.1. DESCRIPTION OF INVESTIGATIONAL PRODUCT

KPI-121 contains submicron particles of loteprednol etabonate suspended in a formulation consisting of excipients that have been used in other FDA-approved ophthalmic products. Kala is developing this improved loteprednol etabonate formulation for the treatment of postoperative anterior segment inflammation and pain.

KPI-121 is a sterile, aqueous submicron suspension of loteprednol etabonate and will be filled in a white, low-density polyethylene plastic bottle with a white, controlled-drop polyethylene tip and a polypropylene cap. The bottle will be a 7.5 mL dropper bottle; the fill volume will be determined after manufacturing trial runs, and will be in the range of 5.0 to 6.0 mL of product.

For this trial, KPI-121 drug product will be supplied in two strengths: 0.25% and 1.0%. Each milliliter of KPI-121 0.25% drug product contains 2.5 mg loteprednol etabonate as the active ingredient; each milliliter of KPI-121 1.0% drug product contains 10 mg loteprednol etabonate as the active ingredient. Inactive ingredients in KPI-121 drug products are [REDACTED] as preservative.

KPI-121 suspensions are essentially isotonic and are buffered to maintain a power of hydrogen (pH) of 5.0 – 7.0.

There are two placebo controls that have the same composition as KPI-121 drug products but do not contain loteprednol etabonate. Placebo A contains [REDACTED]. Both placebo controls also contain [REDACTED] as preservative. The placebo controls are essentially isotonic and are buffered to maintain pH 5.0 – 7.0. They are sterile, aqueous solutions supplied in the same white, low-density polyethylene plastic bottle with the same white, controlled-drop polyethylene tip and white polypropylene closure as KPI-121 drug products.

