3. TRIAL DESIGN

3.1. ENDPOINTS

3.1.1. Efficacy Endpoints

3.1.1.1. Primary Efficacy Endpoints

The primary endpoints of this study will be evaluated using hierarchical statistical testing in the following sequence:

- (1) the difference in the proportion of study eyes with complete resolution of anterior chamber cells (grade = 0) at postoperative Day 8 maintained through end of study and no need for rescue medication for KPI-121 0.25% QID compared to placebo;
- (2) the difference in the proportion of study eyes with complete resolution of anterior chamber cells (grade = 0) at postoperative Day 8 maintained through end of study and no need for rescue medication for KPI-121 1.0% BID compared to placebo;
- (3) the difference in the proportion of study eyes with complete resolution of pain (grade = 0) at postoperative Day 8 maintained through end of study and no need for rescue medication for KPI-121 1.0% BID compared to placebo; and
- (4) the difference in the proportion of study eyes with complete resolution of pain (grade = 0) at postoperative Day 8 maintained through end of study and no need for rescue medication for KPI-121 0.25% QID compared to placebo.

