3.2.2. Study Product

KPI-121 drug product will be supplied in two strengths: 0.25% and 1.0% as a suspension in identically packaged opaque dropper bottles. KPI-121 drug product is a sterile, aqueous, submicron suspension of loteprednol etabonate and will be supplied in a 7.5 mL, white, low-density polyethylene plastic bottle with a white, controlled-drop polyethylene tip and a white polypropylene cap.

Subjects randomized to placebo control arms will receive the same bottles containing all components at the concentrations used in the KPI-121 drug product with the exception of the active component, loteprednol etabonate. Prior to each instillation of study product, subject will shake the study product bottle.

TABLE 1: COMPOSITIONS OF KPI-121 DRUG PRODUCTS

Ingredient	Function	0.25%	1.0%
		Drug Product	Drug Product
		Concentration (% w/v)	
Loteprednol etabonate	Active pharmaceutical ingredient	0.25	1.0
[REDACTED]	[REDACTED]	[REDACTED]	[REDACTED]
[REDACTED]	[REDACTED]	[REDACTED]	[REDACTED]
[REDACTED]	[REDACTED]	[REDACTED]	[REDACTED]
[REDACTED]	[REDACTED]	[REDACTED]	[REDACTED]
[REDACTED]	[REDACTED]	[REDACTED]	[REDACTED]
[REDACTED]	[REDACTED]	[REDACTED]	[REDACTED]
[REDACTED]	[REDACTED]	[REDACTED]	[REDACTED]

TABLE 2: COMPOSITION OF PLACEBO A AND PLACEBO B

Ingredient	Function	Placebo A	Placebo B
		Concentration (% w/v)	
[REDACTED]	[REDACTED]	[REDACTED]	[REDACTED]
[REDACTED]	[REDACTED]	[REDACTED]	[REDACTED]
[REDACTED]	[REDACTED]	[REDACTED]	[REDACTED]
[REDACTED]	[REDACTED]	[REDACTED]	[REDACTED]
[REDACTED]	[REDACTED]	[REDACTED]	[REDACTED]
[REDACTED]	[REDACTED]	[REDACTED]	[REDACTED]
[REDACTED]	[REDACTED]	[REDACTED]	[REDACTED]
[REDACTED]	[REDACTED]	[REDACTED]	[REDACTED]

The study product kit consists of a box of randomized study product that contains two dropper bottles of study product. At Visit 3, eligible subjects will receive one bottle of study product. The second bottle will be retained at the site and provided to the subject, in the event the subject needs additional study product during the treatment period. The box label will contain the following information: sponsor name, protocol and medicinal number, storage temperature and required statement(s) per the appropriate regulatory agency. The dropper bottle contained within the box will be labeled with the following information: sponsor name, protocol number and medicinal number.

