5.1.3. Visit 3: Randomization Visit (Day 1)

The randomization visit will occur 1 day after Visit 2/Surgery Visit. This visit should be scheduled in the morning (if possible) to allow for administration of either BID or QID dosing of study product during the day for eligible subjects.

Eligible subjects who meet the randomization criteria ([Section 4.3](#)) will continue in the study. The following will be performed/assessed:

- Use of any concomitant medications since the last visit
- Occurrence of any AEs since the last visit (**NOTE:** Expected changes or the presence of inflammation resulting from routine uncomplicated cataract surgery will not be captured as AEs.)
- Subject-Rated Ocular Pain Assessment
- Snellen Distance VA by pinhole method
- Slit Lamp Biomicroscopy
 - Signs of anterior ocular inflammation (cell and flare grading)
 - Palpebral conjunctival erythema, corneal edema, hyphema, ciliary flush, bulbar conjunctival injection
- IOP Measurement

NOTE: All ocular assessments must be performed in each eye.

- Upon verification of study eligibility ([Section 4.3](#)), all eligible subjects will be randomized to receive four times per day dosing of either 0.25% KPI-121 drug product or Placebo A **OR** two times per day dosing of either 1.0% KPI-121 drug

product or Placebo B. The following will be performed for all randomized subjects:

- The first dose of double-masked study product will be administered in the clinic under the supervision of designated study personnel. Prior to administration of study product, subjects will be reminded on the proper method for instillation including but not limited to shaking study product bottle prior to each instillation. Since subjects will receive one (1) dose of study product in the clinic, they will self-administer at most three (3) additional doses of study product on the first day if assigned to the QID groups or one (1) additional dose of study product if assigned to the BID dosing group.
- Assess the occurrence of any AEs after study product administration
- Study product kits and instructions for administration will be dispensed
- Subjects will be scheduled to return for Visit 4 on Day 4 \pm 1 day.

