9.1.2. Analysis of Efficacy

The primary analysis population will be the Intent-to-Treat (ITT) population, defined as all subjects randomized. A subset of efficacy analyses will be examined for the Efficacy Evaluable (EE) population defined as all subjects who were randomized, completed 14 days of study product use, had complete data at the Day 8 visit and did not have significant protocol deviations.

The primary analysis of all ophthalmic efficacy measures will be based on a single study eye for each subject. Each subject's study eye will be defined as the surgery eye.

The set of primary endpoints, using hierarchical statistical testing, is (1) the difference in the proportion of study eyes with complete resolution of anterior chamber cells (grade = 0) at postoperative Day 8 maintained through end of study and no need for rescue medication for KPI-121 0.25% QID compared to placebo; (2) the difference in the proportion of study eyes with complete resolution of anterior chamber cells (grade = 0) at postoperative Day 8 maintained through end of study and no need for rescue medication for KPI-121 1.0% BID compared to placebo;; (3) the difference in the proportion of study eyes with complete resolution of pain (grade = 0) at postoperative Day 8 maintained through end of study and no need for rescue medication for KPI-121 1.0% BID compared to placebo; and (4) the difference in the proportion of study eyes with complete resolution of pain (grade=0) at postoperative Day 8 maintained through end of study and no need for rescue medication for KPI-121 0.25% QID compared to placebo.

The following scoring scale for anterior chamber cells will be used:

- 0 = No cells seen
- 1 = 1 - 5 cells
- 2 = 6 - 15 cells
- 3 = 16 - 30 cells
- 4 = greater than 30 cells

The following scoring scale for ocular pain will be used:

- 0 = None
- 1 = Minimal
- 2 = Mild
- 3 = Moderate
- 4 = Moderately Severe
- 5 = Severe

If the two placebo groups demonstrate no statistically significant difference, they will be pooled for analysis.

Using the hierarchical testing scheme, the first test will be the difference in the proportion of study eyes with complete resolution of **anterior chamber cells** (grade = 0) at postoperative Day 8 between the pooled placebo control group and the KPI-121 0.25% QID group using the chi-squared statistic.

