If this test is statistically significant at the two-sided $\alpha = 0.05$ level in favor of the KPI-121 0.25% QID group, then the difference in the proportion of study eyes with complete resolution of **anterior chamber cells** (grade = 0) at postoperative Day 8 between the pooled placebo control group and the KPI-121 1.0% BID group will be tested using the same statistic.

If this test is statistically significant at the two-sided $\alpha = 0.05$ level in favor of the KPI-121 1.0% BID group, then the difference in the proportion of study eyes with complete resolution of **pain** (grade = 0) at postoperative Day 8 between the pooled placebo control group and the KPI-121 1.0% BID group will be tested using the same statistic.

If this test is statistically significant at the two-sided $\alpha = 0.05$ level in favor of the KPI-121 1.0% BID group, then the difference in the proportion of study eyes with complete resolution of **pain** (grade = 0) at postoperative Day 8 between the pooled placebo control group and the KPI-121 0.25% QID group will be tested using the same statistic.

Secondary endpoints will be the proportion of study eyes with complete resolution (grade = 0) of anterior chamber cells (scale 0-4) and complete resolution (grade = 0) of pain (scale 0-5) at Day 8 and at Day 15.

Additional secondary endpoints are composite mean scores of anterior chamber cell and pain grades which will be summarized for each study group at each visit.

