9.2. SAMPLE SIZE ESTIMATION

A two group chi-squared test with a 0.05 two-sided significance level will have 91% power to detect the difference between a proportion of responders in either of the active dosing regimen groups of 0.31 and a combined placebo group proportion of 0.14 when the sample size in each group is 134.

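### Pooling of Placebo A and B depends on an undefined pre-test of about 67 v 67 eyes, and no primary comparator is given if that test is significant

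*Combined protocol and SAP*

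**What the plan says.** The pooling rule appears in Section 9.1 and again in Section 9.1.2: "If the two placebo groups demonstrate no statistically significant difference, they will be pooled for analysis". Neither place adds an endpoint, a statistic, a level, an analysis set or an alternative.

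The hierarchy in Section 9.1.2 then takes pooling as done. The first test is of resolution ("grade = 0) at postoperative Day 8 between the pooled placebo control group and the KPI-121 0.25% QID group using the chi-squared statistic"). The 1.0% BID steps read "between the pooled placebo control group and the KPI-121 1.0% BID group will be tested using the same statistic", and the last step again uses the pooled group. Section 9.2 gives 91% power against "a combined placebo group proportion of 0.14 when the sample size in each group is 134". The endpoint definitions in Section 3.1.1.1 are neutral on which placebo is meant, for example "no need for rescue medication for KPI-121 0.25% QID compared to placebo".

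The two placebos are distinct arms. Section 5.1.3 says "all eligible subjects will be randomized to receive four times per day dosing of either 0.25% KPI-121 drug product or Placebo A", with Placebo B paired likewise with 1.0% BID. Section 1.1 says "There are two placebo controls that have the same composition as KPI-121 drug products but do not contain loteprednol etabonate". Their compositions (Section 3.2.2, "TABLE 2: COMPOSITION OF PLACEBO A AND PLACEBO B") are redacted in the public version.

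**The concern.** A rule with two outcomes is written for only one of them. If Placebo A and Placebo B differ significantly, the condition for pooling fails, yet every primary test is defined against the pooled group. Test 1 then has no comparator, and tests 2 to 4 depend on it. Several choices would be open at that point: own-regimen placebo, pooling anyway, or declaring the hierarchy stopped. These can give different answers, and the choice would be made after seeing the placebo results.

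The pre-test is not defined either. Cells and pain could give different pooling decisions, and the text does not say whether the rule is applied once or for each endpoint. Section 9.3 treats p-values outside the hierarchy as descriptive, although this one would select the primary comparator.

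A non-significant result in two arms of about 67 is also weak evidence that the placebos behave alike, so the rule does little to justify pooling even when it permits it.

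**Working it through.** **Inputs.** From the document: about 402 randomized at approximately 2:2:1:1 (Sections 1.4, 3.2.1); responder rates 0.31 active and 0.14 combined placebo, two-sided 0.05 chi-squared test, 134 per group (Section 9.2). Assumed, because the document does not say: the pre-test is an uncorrected Pearson chi-square at 0.05 on the test 1 endpoint, and, where a fallback is used, it is the own-regimen placebo. Separate rates for A and B are not given, so all unequal pairs below are illustrative.

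**Arm sizes.** 402 × 2/6 = 134 per active arm; 402 × 1/6 = 67 per placebo arm; 67 + 67 = 134 pooled.

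**The plan's own figure.** Power = Φ((|p₁ − p₂| − 1.96·s₀)/s₁), with s₀ from the pooled proportion and s₁ from the separate proportions.
- Pooled placebo, 134 v 134: mean rate 0.225; s₀ = √(0.225 × 0.775 × 2/134) = 0.0510; s₁ = √((0.31 × 0.69 + 0.14 × 0.86)/134) = 0.0499; (0.17 − 0.1000)/0.0499 = 1.40; power 91.9% (exact binomial 92.5%). The stated 91% is reproduced, but only with the pooled placebo.
- Own-regimen placebo, 134 v 67: mean rate (134 × 0.31 + 67 × 0.14)/201 = 0.2533; s₀ = 0.0651; s₁ = 0.0583; (0.17 − 0.1276)/0.0583 = 0.73; power 76.7% (exact 77.9%).

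**Base case, A = B = 0.14, exact enumeration over all outcomes.** The pre-test is significant in 4.84% of trials (2.83% with Fisher's exact test).

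| What follows a significant pre-test | Test 1 power | Tests 1 and 2 jointly | Favourable-side error, all rates 0.14 |
|---|---|---|---|
| Pooled regardless | 92.5% | 87.0% | 2.5% |
| Own-regimen fallback | 91.1% | 84.2% | 3.0% |
| No test (extreme bound) | 88.0% | 82.8% | 2.3% |

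**Unequal placebos (assumed rates, mean 0.14), active 0.31.**

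| A / B | Pre-test significant | Test 1 power, always pooled | Test 1 power, pre-test with own-regimen fallback |
|---|---|---|---|
| 0.16 / 0.12 | 9.9% | 92.5% | 86.3% |
| 0.12 / 0.16 | 9.9% | 92.5% | 93.0% |
| 0.18 / 0.10 | 26.1% | 92.5% | 74.7% |
| 0.10 / 0.18 | 26.1% | 92.5% | 94.8% |

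The direction depends on which placebo is higher. At 0.18/0.10 the own-regimen test alone has 51.7% power, because the true own-regimen effect is only 0.31 − 0.18 = 0.13. Much of the loss there is a smaller effect, not the missing rule.

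**What non-significance shows.** Pre-test power is 38% for a 10-point difference (0.19 v 0.09). As an example, take 13/67 (19.4%) v 6/67 (9.0%). With pooled rate 19/134 = 0.1418, chi-square = 0.1045²/(0.1418 × 0.8582 × 2/67) = 3.0, below 3.84. The difference is 10.4 points, with 95% CI 10.4 ± 1.96 × 5.96, or −1.2 to 22.1. The rule would pool these arms.

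**Error when the active arm equals its own placebo but the placebos differ.** The pooled rate is (0.18 + 0.10)/2 = 0.14, so the pooled contrast is off by half the difference, here 4 points. Favourable-side error of test 1 is:

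| A / B | Always pooled | Pre-test, own-regimen fallback | Own-regimen only |
|---|---|---|---|
| 0.18 / 0.10 | 14.1% | 11.1% | 2.2% |
| 0.10 / 0.18 | 0.2% | 1.9% | 2.1% |

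The pre-test removes little of the error at 0.18/0.10.

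**The case against.** The strongest reply is that the effect is small on the document's own inputs. At 0.14 in both placebos, with the own-regimen fallback, test 1 power is 91.1%, which still meets the stated 91%. The large figures need placebo differences of 8 to 10 points between two drug-free vehicles, for which the document gives no evidence. This stands, and it limits the severity.

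A second reply is that the missing details can be inferred. Chi-squared and 5% are used throughout Sections 9.1.2 to 9.3, and the regimen pairing in Section 5.1.3 points to the own-regimen placebo as the natural fallback. That narrows the room for choice. However, the chi-squared statistic is specified for active v pooled placebo, not for A v B, and the pairing describes randomization. Endpoint, once-or-per-endpoint use and the alternative comparator remain unstated.

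Third, Section 6.5 keeps the codes masked until database lock, and Section 9.5 refers to a statistical analysis plan, so the rule could be completed in time. It could, but nothing in the supplied document shows that it was.

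Finally, dropping the pre-test removes the plan's only check on placebo differences, and the weakness of a non-significant result is no argument for pooling without any test. This is fair. It is why unconditional pooling needs a written justification and an own-regimen sensitivity analysis beside it.

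**Conclusion.** The concern holds. The primary analysis contains a data-dependent branch with no stated comparison, and that branch blocks the test that gates the other three. It should be fixed, but it does not undermine the design.

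At the documented rate of 0.14 the branch is rare (4.8%, or 2.8% with Fisher's exact test). It costs between 1.4 and 4.5 points of test 1 power (92.5% − 91.1% and 92.5% − 88.0%), and it barely moves the error rate. With assumed placebo differences of 4 and 8 points the branch is reached in 9.9% and 26% of trials, and the consequence can go either way. These figures rest on an assumed pre-test and, where stated, an assumed fallback. The absence of a comparator rests on the text alone.

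**What to change.** Before the codes are released, delete the pooling condition from Sections 9.1 and 9.1.2 and name one comparator.

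1. **Preferred: combined placebo.** This is what Section 9.2 and the four test steps already assume. Add a written justification covering both dosing regimen and composition; the compositions are redacted here, so this review cannot judge it. For each primary endpoint, pre-specify each active arm v its own-regimen placebo (134 v 67, with 95% CI) as a sensitivity analysis, and report the A and B rates descriptively. Cost: wording only, no extra patients. Downside: if the placebos truly differ, the pooled contrast is biased by half the difference (14.1% v 11.1% error at 0.18/0.10 above). The own-regimen contrast makes that visible.
2. **If pooling cannot be justified: own-regimen placebo as primary comparator.** Restate power as about 77% to 78% per test at 0.31 v 0.14. Power for tests 1 and 2 jointly falls to about 61% at 402 randomized. Restoring 91% per test needs about 126 eyes per placebo arm, or 2 × 134 + 2 × 126 = 520 randomized.
3. **If the pre-test is kept:** state its endpoint, statistic and level, say whether it is run once or for each endpoint, and name the own-regimen placebo as the fallback. Cost: wording only. This closes the undefined branch but leaves the comparator dependent on the data.
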